3.4 Study Arms

This study will include the following study arms:

Previously Treated Patients:

Arm 1: Subjects who have completed Study CSL654_3001 Arm 1, Study CSL654_3002, or any other CSL-sponsored rIX-FP (CSL654) lead-in study will administer rIX-FP once every 7, 10 or 14 days.

Arm 2: Subjects who were enrolled in Study CSL654_3001 Arm 2 and have <26 weeks of experience with rIX-FP will administer rIX-FP once every 7 days. Subjects who have ≥26 weeks of experience with weekly prophylaxis rIX-FP will administer rIX-FP once every 14 days.

Arm 3: Subjects who have not previously completed a CSL-sponsored rIX-FP lead-in study and who are scheduled to have a major non-emergency surgery within approximately 8 weeks from receiving the first rIX-FP injection (i.e., during the pharmacokinetics [PK] evaluation period) will administer rIX-FP once every 7 days until the month-6 visit.

After the month-6 visit, all subjects (Arms 1, 2, and 3) will administer rIX-FP once every 7, 10, 14 days, 21 days, or 3 times per month for approximately 30 months.

Note: All subjects in Arm 3 will undergo an initial rIX-FP (100 IU/kg) PK evaluation period and complete a surgery substudy before having the option to start routine prophylaxis. In addition, a subcutaneous (SC) substudy will evaluate the safety and PK of SC administration of rIX-FP in adults with severe hemophilia B who are enrolled in the main CSL654_3003 study.

Previously Untreated Patients:

Arm 4: PUPs with severe Hemophilia B (coagulation factor IX (FIX) activity ≤2%) who have never been treated with FIX clotting factor products (except previous exposure to blood components) will be enrolled. Subjects in Arm 4 will administer rIX-FP as weekly prophylaxis and/or on-demand during the first 12 months, and then continue on weekly routine prophylaxis.

This SAP is focusing on the statistical analyses on patients in Arm 4.

3.5 Schedule of Assessments

The Schedule of Assessments for the treatment period (Day 1 to End of Study) during routine prophylaxis for Arms 1, 2, and 3 is provided in [Protocol CSL654_3003 Table A](#), and in [Figure 2](#) of this SAP. The Schedule of Assessments during the PK Period is provided in [Protocol CSL654_3003 Table B](#), and [Figure 3](#) of this SAP. Additional details for subjects in Arm 3 are provided in [Figure 4](#). The Schedule of Assessments for subjects in Arm 4 is provided in [Protocol CSL654_3003 Table D](#), and [Figure 5](#) in this SAP. The Schedule of

Assessments for major surgery or minor surgery are provided in [Protocol CSL654_3003 Appendix 1](#), and the Schedule of Assessments for the SC substudy is provided in [Protocol CSL654_3003 Appendix 2](#).

Figure 2. Schedule of Assessments: Treatment Period (Arms 1, 2, and 3)

Assessments	Day 1 ^B Arm 1 & 2	Month ^A						50 EDs ^D	End of Study
		3 ^C	6 ^L	9 ^C	12	18, 30, 42, 54	24, 36, 48, 60		
Informed consent	X								
Demographics, lead-in study data	X								
Eligibility assessment	X								
Social and physical activity	X		X		X	X	X		X
Relevant medical history ^E	X								
Physical examination	X				X		X		X
Vital signs	X				X		X		X
Body weight and height ^F	X	X	X	X	X	X	X		
Blood biochemistry and hematology (LL)	X				X				X
Inhibitors against FIX (CL)	X		X		X	X	X	X	X
Ab against rIX-FP & CHO cell proteins (CL) ^G	X				X		X	X	X
Plasma FIX activity (CL)	X ^M		X		X	X	X		
Plasma FIX activity (LL)			X		X				
Retain blood sample ^H									X
Dispense subject eDiary	X								
Review subject eDiary		X	X	X	X	X	X		X
Assess treatment efficacy for a major bleed		X	X	X	X	X	X		X
Review treatment regimen ^I			X		X	X	X		
Hemo-Sat questionnaire ^J					X				
CCI					X				
Retrieve eDiary									X
Adverse events		-----On an ongoing basis----->						X	X ^K
Concomitant therapy		-----On an ongoing basis----->						X	X

Ab = antibody; CHO = Chinese hamster ovary; CL = central laboratory; ED = exposure day; eDiary = electronic diary; FIX = coagulation factor IX; LL = local laboratory; CCI = [redacted]; rIX-FP = recombinant coagulation factor IX albumin fusion protein.

Notes to the schedule of assessments:

- A: Time window: ± 2 weeks. All visits should occur within 2 calendar days before the next scheduled prophylactic administration of rIX-FP. A month is 28 days.
- B: Day 1 assessments to be completed only by subjects in Arms 1 or 2. Data that will be transferred from the end of study visit or earlier visit (where relevant) of the lead-in study include demographics, rIX-FP EDs, age cohort in lead-in study, arm in lead-in study, social and physical activity, laboratory assessments (serum biochemistry, hematology), vital signs, physical examination, body height and weight, and antibody assessments (inhibitors against FIX, antibodies against rIX-FP & CHO cell-derived proteins), plasma FIX activity (in subjects from CSL654_3001 study only), adverse events, and concomitant therapy.
- C: For subjects from lead-in Study CSL654_3001 Arm 1, the month 3 and month 9 visits may be conducted via telephone, if the investigator deems that there is no safety risk to the subject. For subjects from lead-in Study CSL654_3001 and CSL654_3002, the month 9 visit may be conducted via telephone, if the investigator deems that there is no safety risk to the subject. The month 3 visit may be omitted for subjects in Arm 2 who have attended a follow-up after visit in the previous 3 months to transition from a 7-day rIX-FP treatment interval to a 14-day rIX-FP treatment interval.
- D: Visit to occur within a month after a subject has experienced a total of 50 rIX-FP EDs in this extension study. If the 50 EDs visit is to occur within 3 months of a follow-up visit, the scheduled follow-up visit may be omitted by conducting all follow-up assessments, in addition to assessments required for the 50 EDs visit, during the 50 EDs visit.
- E: Record genotype and current joint score including scoring system and date of the assessment.
- F: Height to be recorded on day 1 and thereafter at annual intervals only (ie, month 12, 24, etc). Height measurements on the month 12, 24, 36, and 48 visits are optional for subjects ≥ 18 years of age. Measurement of body weight may be omitted at month 3 and month 9 if the visit is conducted via telephone.
- G: A sample that tests positive for antibodies against rIX-FP will be retested to discriminate between plasma-derived FIX, recombinant FIX and albumin antibodies.
- H: Retain samples will be collected for potential serology testing at a later date.
- I: Investigator to review treatment efficacy and change treatment regimen (dose and / or treatment interval), if necessary.

CCI

- K: The observation period for adverse event (and serious adverse event) reporting in an individual subject will start at the time of giving written informed consent for participation in the current study and finish with the end of study visit. However, adverse events ongoing at the end of study visit will be followed until resolution or 30 days after the final administration of rIX-FP during this study, whichever is sooner.
- L: Arm 2 Subjects should attend an unscheduled visit and complete assessments as specified for the 6-month visit if they are to switch to a 14-day treatment interval before completion of the 6-month period. Under such circumstances, the 3-month visit may be omitted.
- M: Sample collected in subjects coming from Study CSL654_3002 after consenting for CSL654_3003.

Figure 3. Schedule of Assessments: Pharmacokinetic Period

Assessments	Before injection	50 IU/kg (Arm 4) or 100 IU/kg rIX-FP PK Visit ^A					
		0 hour (injection)	30 min	72 hours ^B (3 days)	168 hours ^C (7 days)	336 hours ^D (14 days)	504 hours ^D (21 days)
Time Window	< 12 hours before injection		± 5 min	± 24 hrs	± 24 hrs	± 24 hrs	± 24 hrs
Weight and height	X						
Plasma FIX level (central)	X		X	X	X	X	X
Retain blood sample ^E	X						
Administration of rIX-FP		X					
Dispense subject eDiary ^F		X					
Training of self-administration ^F		X	X	X	X		
Adverse events		-----On an ongoing basis----->					
Concomitant therapy		-----On an ongoing basis----->					

eDiary = electronic diary; FIX = coagulation factor IX; PK = pharmacokinetic; rIX-FP = recombinant coagulation factor IX albumin fusion protein.

- A: 100 IU/kg PK completed only by subjects in Arm 3 (no subjects in France may enroll in Arm 3) or subjects ≥18 years who have completed at least 6 months of treatment and planning to begin routine prophylaxis treatment using a 21-day treatment interval for the first time. Subjects in France may not take part in the 21 day treatment regimen. The PK evaluation should be performed after a washout period of at least either 4 days for a current marketed FIX product (ie, subjects in Arm 3 (no subjects in France may enroll in Arm 3) or 14 days for rIX-FP (subjects currently being treated with rIX-FP). 50 IU/kg PK completed by subjects in Arm 4 (see Table D for assessments prior to rIX-FP injection). The investigator may also choose to complete a PK assessment of 50, 75 or 100 IU/kg (as appropriate) rIX-FP with selected time points before starting surgical prophylaxis with rIX-FP, at the investigator's discretion or CSL's request, or in the event of (but not limited to) poor efficacy or suspicion of inhibitor development. Samples may be tested in the local laboratory in addition to the central laboratory. Subjects in France may be discontinued from receiving the study product and participating in any further study procedures if the subject is confirmed to have developed an inhibitor against FIX with a titer > 5 BU/mL.
- B: Optional time point for subjects planning to be switched to a 21-day treatment interval, and Arm 4.
- C: Optional time point for Arm 4 subjects.
- D: Optional time point for subjects in Arm 3 before major surgery (No subjects in France may enroll in Arm 3). Not done for Arm 4.
- E: Retain samples will be collected before the first injection of rIX-FP (subjects in Arm 3 only, excludes subjects in France) for potential serology testing at a later date.
- F: Subjects in Arm 3 only (subjects in France may not enroll in Arm 3). Before completion of the PK evaluation period (at a time point determined by the investigator), the eDiary should be dispensed and subjects should be trained on injection technique, dosing regimen, and use of the eDiary.

Figure 4. Schedule of Assessments: Subjects in Arm 3 (No Subjects in France May Enroll in Arm 3)

	Screening	PK Period	Before surgery	Surgery Substudy	Day 1 ^A Arm 3	Treatment Period
Time window	-1 to -28 days		7 to 56 days after PK injection	Surgery day to 28 ± 7 days after surgery		
Assessments						
Informed consent	X	Complete Schedule of Assessments: Pharmacokinetic Period (Table B)		Complete Schedule of Assessments: Surgery Substudy – Major Surgery		Complete Schedule of Treatment Period Assessments: Treatment Period (Table A)
Demographics	X					
Eligibility assessment	X					
Social and physical activity	X					
Relevant medical and treatment history ^B	X					
Physical examination	X					
Vital signs	X					
Body weight and height	X					
Blood biochemistry and hematology (LL)	X					
Inhibitors against FIX (CL)	X					
Ab against rIX-FP & CHO cell proteins (CL) ^D	X					
Plasma FIX activity (CL and LL)	X					
Begin prophylaxis treatment with rIX-FP					X ^E	
Adverse events	X		X		X	
Prior / concomitant therapy	X		X		X	

Ab = antibody; CHO = Chinese hamster ovary; CL = central laboratory; eDiary = electronic diary; FIX = coagulation factor IX; LL = local laboratory; PK = pharmacokinetics; rIX-FP = recombinant coagulation factor IX albumin fusion protein.

Notes to the schedule of assessments:

- A: The Day 1 visit should occur after completion of the surgery substudy and should occur at the same time as the End of Surgery Substudy visit.
- B: Record history of hemophilia B including genotype and current joint score (including scoring system and date of the assessment), and treatment history with a marketed FIX.
- C: Body weight only.
- D: A sample that tests positive for antibodies against rIX-FP will be retested to discriminate between plasma-derived FIX, recombinant FIX and albumin antibodies.
- E: Subjects in Arm 3 (No subjects in France may enroll in Arm 3) who require physical therapy (ie, rehabilitation after surgery), may administer rIX-FP as preventative treatment (no more than once per week) in addition to the administration of rIX-FP as routine prophylaxis. Preventative treatment before physical therapy is permitted only during the first 3 months of the treatment period.

Figure 5. Schedule of Assessments: Subjects in Arm 4

Assessments	Screen ^B up to 28 days	(PK ^A)				Months ^I (±1 week)												Months (±2 week)						50 EDs	EoS ^L					
		Prior dose	30±5 mins	Day 3	Day 7	1	2	3	4	5	6	7	8	9	10	11	12	15	18	21	24	27	30			33				
Informed consent	X																													
Demographics	X																													
Eligibility assessment	X																													
Relevant medical history	X																													
Physical examination	X					X	X	X	X	X	X	X	X	X	X	X	X	X	X	X	X	X	X	X	X	X	X			
Vital signs ^C	X					X	X	X	X	X	X	X	X	X	X	X	X	X	X	X	X	X	X	X	X	X	X			
Body weight and height	X	X				X	X	X	X	X	X	X	X	X	X	X	X	X	X	X	X	X	X	X	X	X	X			
Biochemistry&hematology ^D	X ^E																				X						X			
Inhibitors against FIX (CL)	X ^E					X	X	X	X	X	X			X			X		X	X	X	X	X	X	X	X	X			
Ab to rIX-FP/CHO (CL) ^F	X ^E													X			X			X					X	X	X			
Plasma FIX activity (CL) ^H		X	X	X	X	X	X	X			X					X				X							X			
Plasma FIX activity (LL)	X ^J																													
Retain blood sample ^G		X																									X			
Dispense subject eDiary ^K																									X					
Review subject eDiary						----- On an ongoing basis during eDiary usage -----																								X
Review treatment efficacy						----- On an ongoing basis -----																								X
Adverse events		----- On an ongoing basis -----																												
Concomitant therapy		----- On an ongoing basis -----																												

Ab = antibody; CHO = Chinese hamster ovary; CL = central laboratory; eDiary = electronic diary; FIX = coagulation factor IX; LL = local laboratory; PK = pharmacokinetics; rIX-FP = recombinant coagulation factor IX albumin fusion protein; EoS=End of Study.
 Subjects will be treated in the study center or medical facility under medical supervision during the initial 10 to 20 treatment with rIX-FP. The first 2 infusions must be monitored on-site for at least 3 hours.

- A: PK can start at Day 1 as the first dose or/and during the study after ≥7 days washout from the previous rIX-FP dose, when the subject is in non-bleeding state. See Table D for PK sampling time points. (Day 1 is the day subject receives his first dose with rIX-FP)
- B: Tests that require blood sample for screening period (from ICF day to Day 1 prior to dose) can be divided to multiple days or combined with Day 1 tests. The screening day can be the same day for first dose of rIX-FP (either on-demand, prophylaxis or PK dose).
- C: Vital signs include blood pressure, temperature and heart rate.
- D: Includes liver and renal function test (Albumin, Alanine Aminotransferase, Aspartate Aminotransferase, Alkaline Phosphatase, Bilirubin, Direct Bilirubin, Protein, Blood Urea Nitrogen or Urea, and Creatinine).
- E: Documented biochemistry & hematology results from 6 months prior to screening are acceptable; otherwise, samples may be collected during the screening period or at Day 1. Samples for antibodies/inhibitor must be collected during the screening period or prior to first dose of rIX-FP.
- F: A sample that tests positive for antibodies against rIX-FP will be retested to discriminate between pdFIX, rFIX and albumin antibodies.
- G: Retain samples will be collected prior to the first dose of rIX-FP for potential serology testing at a later date.
- H: Optional samples at Day 3 or Day 7 of PK assessment, or during the month 1, 2 or 3 for FIX activity if feasible.
- I: If subjects receive treatment for less than 3 doses per month, they may omit the site visit(s) until they received ~5 doses.
- J: FIX activity tested at local Laboratory if no previous FIX data available in medical records.
- K: Subject eDiary may be dispensed once caregiver is trained to administer rIX-FP at home, but not prior to receiving a minimum of 10 infusions at the study center or medical facility under medical supervision.
- L: End of Study for Arm 4 is the Month 36 visit.

3.6 Study Populations

The following analysis populations will be used for the presentation of the statistical analyses in this study.

3.6.1 Screened Population

The screened population will consist of all subjects who provided written informed consent to undergo study screening procedures.

3.6.2 Enrolled Population

The enrolled population will consist of all subjects who were not screen failures.

3.6.3 Safety Population

The safety population will consist of all subjects who received at least 1 dose of rIX-FP in this extension study.

3.6.4 Efficacy Population

The efficacy population will consist of all subjects in the safety population. Data collected in the surgery and subcutaneous substudies will be excluded from analyses of efficacy. Analyses of the surgery and subcutaneous substudies will be reported separately.

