11.2.3 Efficacy Population

The efficacy population will consist of all subjects in the safety population who participate in the non-surgical efficacy portion of the study.

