- Prophylaxis rIX-FP therapy should be restarted as soon after the surgical procedure as medically appropriate. If a subject does not restart prophylaxis, the subject should be withdrawn from the study and the rationale for the decision should be documented in the eCRF. In addition, attempts should be made to complete and document the end of study assessments (main study).

C. End of Participation in the Substudy (Major and Minor Surgery)

The end of substudy participation for an individual subject occurs with the end of the postoperative period, which is defined as completion of the final substudy visit and the resumption of the main study protocol. Subjects in Arm 3 may end participation in the study at this visit or start routine prophylaxis treatment in the main study.

The following procedures will be performed at the final substudy visit:

- Physical examination.
- Vital signs.
- Blood samples for hematology (major surgery only).
- Blood samples for antibodies against rIX-FP and FIX inhibitor (central laboratory).
- Blood sample for FIX activity level (central and local laboratory).
- Record AEs and concomitant therapies.

For some minor surgical procedures, the End of Surgery Substudy visit may be combined with hospital discharge.

D. Discontinuation Procedures for the Substudy (Major and Minor Surgery)

The following assessments must be performed at an early termination visit for any subject who has received rIX-FP and discontinues participation in the study (main study and substudy) prematurely:

- Vital signs.
- Physical examination.
- Blood samples for laboratory safety evaluation (hematology and serum chemistry).
- Blood samples for antibodies against rIX-FP, FIX inhibitor and CHO cells (central lab).
- Blood sample for FIX activity level (central and local lab).
- Retain blood sample.
- Record AEs and concomitant therapies.

STUDY VARIABLES AND METHODS OF ASSESSMENT

For an overview of the study variables and measurement times, see the [Schedule of Assessments: Surgery Substudy – Major Surgery](#) and the [Schedule of Assessments: Surgery Substudy – Minor Surgery](#).

Subject Characteristics

See [Section 10.1](#) for details.

Efficacy Variables

Overview of Variables

The primary clinical efficacy parameters assessed in the study are study product usage and hemostasis assessments by the Investigator.

Primary efficacy variable:

Investigator's evaluation of efficacy of rIX-FP prophylaxis during surgery.

Secondary efficacy variables:

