This document presents the statistical analysis plan (SAP) for CSL Behring GmbH, Protocol No. CSL654_3003: A Phase 3b Open-label, Multicenter, Safety and Efficacy Extension Study of a Recombinant Coagulation Factor IX Albumin Fusion Protein (rIX-FP) in Subjects with Hemophilia B.

This analysis plan is based on the protocol amendment 6 dated 03 February 2020, final electronic case report form (eCRF) dated 17 May 2017, and the SAP version 3 dated 20 April 2018. This SAP contains all analyses for the previously treated patients (PTPs), and the updated contents for the previously untreated patients (PUPs).

In the event that the statistical methods specified in this SAP differ from those specified in the protocol, the statistical methods specified in the SAP will supersede the statistical methods described in the protocol.

2 Study Objectives

- Main Study
 - Primary Objective
 - The primary objective of this study is to evaluate the safety of rIX-FP as measured by new cases of inhibitors against FIX in subjects, including PUPs, with severe hemophilia B. The PK parameters in PUPs will also be collected.
 - Primary Endpoint(s)
 - The total number of subjects who develop inhibitors against FIX during the approximately 5-year participation in this study.
 - PK parameter of incremental recovery (IU/dL per IU/kg) of 50 IU/kg rIX-FP (Arm 4 only)
 - Secondary Objective(s)

[figure not shown]
The secondary objectives of the study are:

 - To evaluate the efficacy of rIX-FP routine prophylaxis when administered at various treatment intervals.
 - To compare the efficacy of rIX-FP routine prophylaxis between 2 different treatment intervals and versus on-demand treatment.
 - To further evaluate the safety of rIX-FP.
 - To evaluate the efficacy of treatment for bleeding episodes in PUPs.
 - Secondary Endpoint(s)
 - Annualized bleeding rate (ABR) for spontaneous treated and total treated bleeds for each assigned treatment interval (7 days, 10 days, 14 days, and 21 days).
 - Comparison of the annualized spontaneous bleeding rate (AsBR) and ABR between:

- 14-day routine prophylactic treatment in this study compared with on-demand only treatment from Study CSL654_3001 Arm 2.
- 7-day prophylaxis regimen with the 14-day prophylaxis regimen.
- 7-day prophylaxis regimen with the extended prophylaxis regimen (10-day or 14-day).
- Total number of exposure days of rIX-FP
- Consumption of rIX-FP during routine prophylaxis expressed as IU/kg per month per subject.

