A comparison of AsBR and ABR will be performed between 14-day prophylaxis treatment in this study compared with on-demand treatment from Study CSL654_3001 (Arm 2) for subjects ≥ 12 years of age. A Wilcoxon signed-rank test will be performed on the matched-pairs at the two-sided 0.05 level to test the hypothesis that the median difference in rates differs from zero. Descriptive statistics will also be provided.

The analysis of AsBR will also be conducted with subjects from both Study CSL654_3001 and the present extension study to assess whether a similar treatment effect exists between the 7-day prophylaxis regimen and the 14-day prophylaxis regimen.

In order to demonstrate that a similar treatment effect also exists for the 14-day prophylaxis regimen and 7-day prophylaxis regimen, the mean AsBR will be compared between the two prophylaxes regimens to evaluate non-inferiority. Following the same clinically acceptable difference used in the CSL654_3001 study, a non-inferiority margin of 6 spontaneous bleeding events/year is used.

The null and alternative hypotheses for the AsBR are as follows:

$$H_0: \mu_{7\text{-day}} - \mu_{14\text{-day}} \leq -6$$

$$H_1: \mu_{7\text{-day}} - \mu_{14\text{-day}} > -6$$

To establish non-inferiority of the 14-day regimen versus the 7-day regimen for the AsBR, the lower confidence limit of the 95% CI, based on a paired t-test, for the difference between the two means (7-day regimen – 14-day regimen) must be greater than -6 spontaneous bleeding events/year. In addition, a 99% CI of the mean difference will be assessed.

The same analyses will be conducted for the comparison of ABR. Furthermore, the non-inferiority analysis of AsBR and ABR between the 14-day or 10-day regimens (combined) and the 7-day regimen will be conducted in a similar manner.

Summaries of ABRs by regimen will be presented from Study CSL654_3003. In addition, when comparing the ABRs between regimens, the bleeding data from the lead-in studies (CSL654_3001 and 3002) and this study will be utilized as applicable.

Additionally, the number and percentage of subjects with no bleeding events, number and percentage of subjects with at least 1 bleeding event (requiring treatment with CSL654 and not requiring treatment with CSL654) will be presented.

Analyses of bleeding rates will be presented overall, by age, and by regimen as applicable. Hypothesis testing will not be applicable for PUPs.

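### SAP 3.6.4 widens the efficacy population without declaring it, so Arm 3 subjects who leave after surgery can enter the zero-bleed percentage with no prophylaxis time behind them

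*SAP*

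**What the plan says.** Protocol 11.2.3 defines the efficacy population by two conditions, membership of the safety population and participation outside surgery: "The efficacy population will consist of all subjects in the safety population who participate in the non-surgical efficacy portion of the study".

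SAP 3.6.4 keeps only the first: "The efficacy population will consist of all subjects in the safety population". It then acts on data, not on subjects: "Data collected in the surgery and subcutaneous substudies will be excluded from analyses of efficacy". SAP 3.6.3 sets the entry bar at a single dose: "The safety population will consist of all subjects who received at least 1 dose of rIX-FP in this extension study". An Arm 3 subject meets it with his initial PK injection.

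Where the two documents differ, the SAP's opening section says that "the statistical methods specified in the SAP will supersede the statistical methods described in the protocol". SAP Section 8 lists departures from the protocol, including one about the three months after surgery, but not this one.

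On leaving after surgery, Protocol Appendix 1, Section C says: "Subjects in Arm 3 may end participation in the study at this visit or start routine prophylaxis treatment in the main study".

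SAP 4.12.3 asks for the "number and percentage of subjects with no bleeding events", together with the matching count of subjects with at least one event. No minimum observation time is attached to either row.

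**The concern.** The condition that the SAP drops is the one that keeps out a subject who was treated only for PK and surgery. Routine prophylaxis is optional for Arm 3. SAP Table 2 runs the surgery period to Day 28 or to the End of Substudy visit, whichever is later. SAP 4.12.1 excludes bleeds in the PK and surgery periods, and SAP 4.12.3 excludes that time from the rates. A subject who leaves at the end-of-substudy visit therefore contributes no time to any prophylaxis regimen, yet he sits in the efficacy population.

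The percentage of bleed-free subjects is a natural headline for a prophylaxis product. If the denominator includes people never observed on prophylaxis, and the program counts the absence of a recorded event as no event, the percentage moves in the favourable direction only. The annualized rate does not offset this. SAP 4.12.3 sets it to missing below 12 weeks on a regimen, and also sets it to missing for a subject with no treated bleeds. As written, the zero-bleed row is then the main place where bleed-free subjects appear, so its denominator needs to be clean.

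**Working it through.** **Inputs**
- Previously treated patients in the final analysis: 83 (Protocol Revision History, Amendment 6).
- Previously untreated patients: at least 13 (Protocol 3.5).
- Planned Arm 3 size: about 10 (Protocol 3.5).
- Expected share of subjects with no bleeds: about half (SAP Section 8, in the reason given for the negative binomial model).
- Default denominator: all subjects in the arm or regimen (SAP 4.1), or the total N (SAP 9.1).
- Display levels: overall, by age and by regimen (SAP 4.12.3); by arm under the general rule in SAP 4.1.
- Number of Arm 3 subjects who leave after surgery, *k*: not stated. Range taken: 0 to 10.

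**Check on the plan's own figure.** 83 + 13 = 96, which matches the planned total in Protocol 3.5. That total is not based on power, and the documents state no figure for the zero-bleed row itself.

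**Formula.** Let *p* be the zero-bleed share among subjects with regimen time. With leavers removed, as under the protocol population, the overall figure is *p*. With leavers kept and counted as bleed-free, it is

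[*p* × (83 − *k*) + *k*] / 83, which exceeds *p* by *k*(1 − *p*)/83.

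**Overall display at *p* = 50%**

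| Leavers *k* | Calculation | Reported share |
|---|---|---|
| 0 | 41.5/83 | 50.0% |
| 1 | (41 + 1)/83 | 50.6% |
| 3 | (40 + 3)/83 | 51.8% |
| 5 | (39 + 5)/83 | 53.0% |
| 10 | (36.5 + 10)/83 | 56.0% |

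**Sensitivity to *p* at *k* = 10.** At *p* = 30% the rise is 10 × 0.7/83 = 8.4 points. At *p* = 70% it is 10 × 0.3/83 = 3.6 points.

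**Arm 3 display (n = 10, *p* = 50%).** The share is [0.5 × (10 − *k*) + *k*]/10: 55% with 1 leaver, 65% with 3, 75% with 5. With 10 it reads 100%, with nobody observed on prophylaxis.

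**By-age display.** Arm 3 enrolls ages 12 to 70 (Protocol 4.1.1), so any effect falls in the column for age 12 and over. The size of that column is not given.

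**What does not move**
- Annualized total and spontaneous rates: missing for a leaver.
- Crude rates: a leaver adds no regimen events and no regimen time.
- Paired comparisons: they need data on two regimens.
- By-regimen displays: a leaver never enters a regimen.

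**The case against.** The strongest reply is that nothing in the SAP says that a subject with no evaluable time is bleed-free. SAP 4.1.5 rules out imputation for withdrawals and missing data apart from partial dates and the derivation of annualized rates, and treating an unobserved subject as a non-bleeder sits badly with that. This stands. A reader might infer that leavers are bleed-free by rule; the documents support only that they can be counted so, because the default denominators include them and no text says how to classify them.

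It is also tempting to say that a leaver must have zero countable bleeds. That goes too far. Surgery falls 7 to 56 days after the PK injection (Protocol Table C), and the Day 14 and Day 21 samples are optional for Arm 3. If the last PK sample is on Day 7 and surgery on Day 56, up to about 56 − 7 = 49 days lie between the two periods. A bleed in that gap is not excluded by SAP 4.12.1 and belongs to no period in SAP Table 2.

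A reader might infer that the secondary endpoints are biased. They are not, for the reasons in the working. What is exposed is a set of descriptive rows outside the listed endpoints.

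A reader might also quote a rise above 8 points. That needs all ten planned Arm 3 subjects to leave and a true share near 30%, whereas the SAP expects about half. The calculation also sets a planned Arm 3 size against a final patient count.

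Finally, SAP 3.1 says that Arms 1 to 3 were already analyzed in a report dated 14 March 2019, and SAP 3.4 says that this version focuses on Arm 4. That limits the practical reach but does not close the point. The SAP still states that it contains all analyses for previously treated patients, and Protocol 14.7 integrates their report into the final one.

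**Conclusion.** The point holds in a limited form. SAP 3.6.4 is wider than Protocol 11.2.3, it takes precedence, and Section 8 does not declare the change. Arm 3 subjects who leave after surgery remain in the efficacy population with no prophylaxis-regimen time, and under the default denominators they can be counted as bleed-free in the overall, by-age and by-arm rows.

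At the SAP's own 50% expectation the overall rise is at most 6.0 points, is 3.0 points with 5 leavers, and is zero if nobody left. These figures assume 83 previously treated patients, about 10 in Arm 3, no gap-period bleed counted against a leaver, and a program that reads no recorded event as no event. The true number of leavers would settle the size, and the documents do not give it.

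**What to change.** - Restore the protocol's participation condition in SAP 3.6.4. Alternatively, leave the population as it is and limit the rows for no bleeding events and at least one bleeding event to subjects with evaluable regimen time outside the PK, surgery and SC periods. The second route is better with the same 12-week minimum as the annualized rate, because otherwise a subject with a few days of prophylaxis would still count as bleed-free.
- List the change of definition in SAP Section 8.
- In the final integrated report, state how many Arm 3 subjects had no such time, and correct the row for previously treated patients if any did. If none did, one line closes the matter.

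The text change is a sentence and a population flag. The cost beyond that is that one already reported descriptive row may need re-running, and the overall bleed-free percentage may become slightly less favourable.
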